6.1 Population characteristics

Refer to the main SAP v2.0 dated 17 MAY 2017.

6.1.1 Additional Summary of Baseline Characteristics

The following baseline cancer characteristics will be summarized for ITT and week 24 analysis set:

- The summary of patients with vertebral bone metastasis at baseline
- The number of subjects with prior local radiotherapy on prostate and prostate gland by intent.

6.1.2 Additional Summary of Prior/Concomitant Bone Health Agent (BHA) use

The number of subjects who used BHA at baseline and during treatment period will be summarized for ITT and week 24 analysis set.

6.2 Efficacy

Refer to the main SAP v2.0 dated 17 MAY 2017.

Pain improvement rate at week 12, week 24, EOT, and overall will be summarized by including all subjects in ITT population as denominator. Same analyses will be repeated for week 24 analysis set.

6.3 Exploratory variables and analyses

Refer to the main SAP v5.0 dated 17 NOV 2017.

6.4 Pharmacokinetics

Not Applicable.

6.5 Safety

Refer to the main SAP v2.0 dated 17 MAY 2017.

6.5.1 Adverse Events

Additional analyses of Adverse Events of Interest

Time to fracture is defined as the time (months) from the first dose date to the date of first fracture. Subjects without fractures are censored at the last visit date during treatment period. Time to fracture will be summarized using Kaplan-Meier estimates. Median survival time together with the 25th and 75th percentiles and associated 80% and 95% Brookmeyer-Crowley confidence intervals (CI) will be presented by treatment arm. Corresponding Kaplan-Meier curves will be generated by treatment arm.

Time to fracture will also be summarized for subjects with/without use of concomitant anti-androgen, enzalutamide and abiraterone during the treatment period using same approach mentioned above, respectively.

A subject listing of fractures will be provided.

7. Document history and changes in the planned statistical analysis

- Main SAP v2.0 dated 17 MAY 2017.

8. References

Refer to the main SAP v2.0 dated 17 MAY 2017.

Title page

A three arm randomized, open-label Phase II study of radium-223 dichloride 50 kBq/kg (55 kBq/kg after implementation of NIST update) versus 80 kBq/kg (88 kBq/kg after implementation of NIST update) , and versus 50 kBq/kg (55 kBq/kg after implementation of NIST update) in an extended dosing schedule in subjects with castration-resistant prostate cancer metastatic to the bone

[Standard dose versus high dose and versus extended standard dose radium-223 dichloride in castration-resistant prostate cancer metastatic to the bone]

Bayer study drug BAY 88-8223 / Radium-223 dichloride / Xofigo

[Study purpose:] Efficacy, dose-finding

Clinical study phase: II **Date:** 08 Oct 2018

Study No.: BAY 88-8223 / **Version:** 2.0
16507

Author: PPD

Confidential

The information provided in this document is strictly confidential and is intended solely for the guidance of the clinical investigation. Reproduction or disclosure of this document, whether in part or in full, to parties not associated with the clinical investigation or its use for any other purpose without the prior written consent of the sponsor is not permitted.

Throughout this document, symbols indicating proprietary names (®, TM) are not displayed. Hence, the appearance of product names without these symbols does not imply that these names are not protected.

This Statistical Analysis Plan is produced on a word-processing system and bears no signatures.
The approval of the Statistical Analysis Plan is documented in a separate Signature Document.

Table of Contents

Title page.....	1
Abbreviations.....	2
1. Introduction.....	2
2. Study Objectives.....	3
3. Study Design.....	4
4. General Statistical Considerations.....	4
5. Analysis Sets.....	4
6. Statistical Methodology.....	4
6.1 Population characteristics.....	4
6.1.1 Additional Summary of Disposition of Subjects.....	4
6.1.2 Additional Summary of Baseline Characteristics.....	4
6.1.3 Additional Summary of Prior/Concomitant Bone Health Agent (BHA) use.....	5
6.1.4 Additional Summary of Post-treatment Bone Radiotherapy Use.....	5
6.2 Efficacy.....	5
6.3 Exploratory variables and analyses.....	5
6.4 Pharmacokinetics.....	5
6.5 Safety.....	5
6.5.1 Adverse Events.....	5
6.5.2 Long Term Adverse Events.....	6
6.5.3 Long Term Safety.....	6
7. Document history and changes in the planned statistical analysis.....	6
8. References.....	6

Abbreviations

AE	Adverse event
BHA	Bone health agent
CI	Confidence interval
CSR	Clinical Study Report
SAP	Statistical Analysis Plan

1. Introduction

This Supplemental Statistical Analysis Plan (SAP) describes analyses that were not included in the main SAP but may be used for submission purposes or CSR.

This Supplemental SAP version 1.0 is a supplement of SAP version 2.0 dated 17 May 2017.

2. Study Objectives

Co-primary objectives:

- To evaluate efficacy as measured by SSE-FS of radium-223 dichloride 50 kBq/kg (55 kBq/kg after implementation of NIST update) every 28 days for up to 6 doses compared to radium-223 dichloride 80 kBq/kg (88 kBq/kg after implementation of NIST update); and
- To evaluate efficacy as measured by SSE-FS of radium-223 dichloride 50 kBq/kg (55 kBq/kg after implementation of NIST update) every 28 days for up to 6 additional doses compared to no further radium-223 dichloride treatment in subjects with CRPC metastatic to the bone who previously received radium-223 dichloride 50 kBq/kg (55 kBq/kg after implementation of NIST update) every 28 days for up to 6 doses, and survived SSE free and are eligible for further radium-223 dichloride treatment.

Secondary objectives:

- To evaluate safety and tolerability
- To evaluate overall survival (OS)
- To evaluate pain improvement rate
- To evaluate time to pain progression
- To evaluate time to first SSE
- To evaluate time to radiological progression
- To evaluate radiological progression-free survival (rPFS)

Exploratory objectives:

- To evaluate quantitated whole body technetium-99 bone scan tumor burden area and index, and determine bone tumor response
- To explore the impact of patient body size on the efficacy and safety of radium-223 dichloride
- Time to increase in physical symptoms of disease based on the NCCN FACT-P Symptom Index-17 (NCCN-FACT FPSI-17) physical disease related symptoms (FPSI-DRS-P) subscale score measured up to Week 48 after the start of treatment
- To evaluate laboratory indicators of efficacy, including:
 - PSA response
 - Time to PSA progression
 - ALP response
 - Time to ALP progression
 - Percentage change in ALP from baseline

- To evaluate change in analgesic use.

3. Study Design

Refer to the main SAP v2.0 dated 17 MAY 2017.

4. General Statistical Considerations

Refer to the main SAP v2.0 dated 17 MAY 2017.

5. Analysis Sets

Refer to the main SAP v2.0 dated 17 MAY 2017.

6. Statistical Methodology

Refer to the main SAP v2.0 dated 17 MAY 2017.

6.1 Population characteristics

Refer to the main SAP v2.0 dated 17 MAY 2017.

6.1.1 Additional Summary of Disposition of Subjects

The number and percentage of subjects entered long-term follow up, completed and discontinued and reason for discontinuation will be presented by treatment group and overall for both ITT and safety analysis set.

6.1.2 Additional Summary of Baseline Characteristics

The following baseline cancer characteristics will be summarized for ITT and week 24 analysis set:

- The summary of patients with vertebral bone metastasis at baseline
- The number of subjects with prior local radiotherapy on prostate and prostate gland by intent.

The following summary tables will be provided for subjects who entered long-term follow up in safety analysis set.

- Demographics
- Baseline prostate cancer characteristics

6.1.3 Additional Summary of Prior/Concomitant Bone Health Agent (BHA) use

The number of subjects who used BHA at baseline and during treatment period will be summarized for ITT and week 24 analysis set. The same summary tables will also be provided for subjects who entered long-term follow up period in safety analysis set.

6.1.4 Additional Summary of Post-treatment Bone Radiotherapy Use

The number of subjects who received bone radiotherapy after last dose of Radium-223 will be summarized for subjects who entered long-term follow up period in safety analysis set.

6.2 Efficacy

Refer to the main SAP v2.0 dated 17 MAY 2017.

Pain improvement rate at week 12, week 24, EOT, and overall will be summarized by including all subjects in ITT population as denominator. Same analyses will be repeated for week 24 analysis set.

6.3 Exploratory variables and analyses

Refer to the main SAP v5.0 dated 17 NOV 2017.

6.4 Pharmacokinetics

Not Applicable.

6.5 Safety

Refer to the main SAP v2.0 dated 17 MAY 2017.

6.5.1 Adverse Events

Additional analyses of Adverse Events of Interest

Time to fracture is defined as the time (months) from the first dose date to the date of first fracture. Subjects without fractures are censored at either end of treatment (EOT) visit date or the last visit date before the start of active follow-up Period if no EOT visit was recorded. Time to fracture will be summarized using Kaplan-Meier estimates. Median survival time together with the 25th and 75th percentiles and associated 80% and 95% Brookmeyer-Crowley confidence intervals (CI) will be presented by treatment arm. Corresponding Kaplan-Meier curves will be generated by treatment arm.

Time to fracture will also be summarized for subjects with/without BHA use at baseline, with/without concomitant use of anti-androgen, enzalutamide, and abiraterone by same approach mentioned above, respectively.

A subject listing of bone fractures occurred after first dose will be provided.

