6.5.2 Long Term Adverse Events

All Bone fracture and bone events occurred after patients entering long-term follow up period will be summarized by NCI-CTCAE toxicity criteria. Same summary will also be provided for serious bone fracture and bone events during long-term follow up period. A listing of bone fracture and bone events will be provided for entire study period and during follow-up period, respectively.

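### Time to fracture has an EOT censoring date for fracture-free subjects but no stated end to the event window, so read literally the Kaplan-Meier curves fall artificially after treatment

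*SAP*

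**What the plan says.** Supplemental SAP v2.0, section 6.5.1, gives the endpoint as: "Time to fracture is defined as the time (months) from the first dose date to the date of first fracture". No sentence ends the event window. The censoring rule covers only subjects who have no fracture: "Subjects without fractures are censored at either end of treatment (EOT) visit date". Where that visit is missing, a fallback date applies, namely the final visit preceding active follow-up. Supplemental SAP v1.0, section 6.5.1, had the same structure with a different date: "Subjects without fractures are censored at the last visit date during treatment period".

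The output is shown by arm: "Corresponding Kaplan-Meier curves will be generated by treatment arm". Medians and quartiles with 80% and 95% intervals are also planned. The curves are repeated by baseline bone health agent use and "with/without concomitant use of anti-androgen, enzalutamide, and abiraterone by same approach mentioned above".

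Fractures after treatment are expected in the data. Section 6.5.1 adds: "A subject listing of bone fractures occurred after first dose will be provided". Section 6.5.2 summarizes fractures in long-term follow-up and adds: "A listing of bone fracture and bone events will be provided for entire study period and during follow-up period, respectively". In the main SAP, section 6.2.1, new symptomatic pathological fractures are also a component of the primary endpoint, which is followed past treatment.

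**The concern.** A Kaplan-Meier estimate needs each subject's time at risk to be set without reference to whether that subject has the event later. Here a subject whose first fracture comes after EOT stays at risk until that fracture, while a subject who never fractures leaves at EOT. Past EOT the risk set therefore consists of people already known to fracture, and the curve has to end at zero.

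EOT comes much earlier with 6 planned doses (Arms A and B) than with 12 (Arm C), so the fall starts earlier in A and B. The by-arm display would then show a fracture advantage for the extended regimen that the rule itself creates. The supplement says its analyses may be used for submission or the study report, and fracture is a safety question that readers will look for with a bone-targeted agent.

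The anti-androgen split has a narrower problem. Under Table 6–1 of the main SAP, concomitant medication includes drugs started on or after first dose (C3, C6). A subject in that group must stay under observation until the drug starts, which credits the group with event-free time. Drugs started earlier and continued (C2, C4) do not raise this.

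**Working it through.** The documents state no figure for time to fracture, so there is none to reproduce.

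**Inputs from the documents.** Dosing is every 4 weeks, 6 doses in Arms A and B and 12 in Arm C (main SAP, section 1). The EOT visit is 30±7 days after last dose (section 4.5.1). Active follow-up runs two years after last dose (section 1). About 120 subjects per arm (360 at 1:1:1, section 3.4).

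**Assumptions not in the documents.** Constant fracture hazard λ, equal in all arms, at 0.5%, 1% or 2% per month; median survival 18 months, so death hazard μ = ln 2/18 = 0.0385 per month; early stopping either none or with a 9-month median.

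**Dates if treatment is completed** (30.44 days per month):
- 6 doses: EOT τ = 5×28 + 30 = 170 days = 5.6 months; end of follow-up C = 140 days + 24 months = 28.6 months.
- 12 doses: τ = 11×28 + 30 = 338 days = 11.1 months; C = 308 days + 24 months = 34.1 months.

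**Rule as written, closed form.** Up to τ the estimate is correct: exp(−λt). After τ those at risk at time t are the subjects who will fracture between t and the earlier of death and C. Their number is proportional to exp(−κt) − exp(−κC), with κ = λ + μ. Hence

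KM(t) = exp(−λτ) × [exp(−κt) − exp(−κC)] / [exp(−κτ) − exp(−κC)],

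which is zero at C whatever λ is. With λ = 0.01 (κ = 0.0485) and t = 12:
- truth: exp(−0.12) = 0.887
- 6 doses: 0.9457 × (0.5587 − 0.2497)/(0.7627 − 0.2497) = 0.570
- 12 doses: 0.8949 × (0.5587 − 0.1911)/(0.5835 − 0.1911) = 0.838

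**Simulation of the same rule**, 400,000 per arm, λ = 1% per month (truth 0.887 at 12 months, 0.787 at 24; true median ln 2/0.01 = 69 months):

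| Planned doses | Stopping | 12 months | 24 months | KM median |
|---|---|---|---|---|
| 6 | all complete | 0.575 | 0.118 | 13.6 |
| 12 | all complete | 0.839 | 0.275 | 18.4 |
| 6 | 9-month median | 0.558 | 0.096 | 13.2 |
| 12 | 9-month median | 0.794 | 0.201 | 17.1 |

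The all-complete rows agree with the closed form within simulation error. Over hazards of 0.5–2% per month, the false median is 12.0–14.0 months for 6 doses and 15.4–19.2 for 12; the true median is 35–139 months. As a gauge only, since the plan has no such test, a two-sided 5% log-rank comparison of A and C at 120 per arm rejects in 25–50% of replicates with no true difference.

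**Matched windows** (1% per month, 9-month median stopping):
- Events and censoring both end at EOT: 12 doses gives 0.895 at 12 months (the value at 11.1 months carried forward), against 0.887; 6 doses gives 0.946 at 6 months (carried from 5.6), against 0.942. Neither curve has support later.
- Events and censoring both run to the end of complete follow-up: 0.887 in both arms at 12 months.
- The illustrative log-rank returns to about 4–6% under either.

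**Incomplete capture after treatment.** If only 10% of post-EOT fractures are recorded (0.5% per month, 9-month median stopping), the rule as written gives 58% and 88% at 12 months, against 59% and 86% with full capture; truth is 94%. The risk set after EOT shrinks along with the events.

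**The case against.** The strongest reply is that an on-treatment analysis was meant. The section sits under adverse events. The main SAP (section 6.4.1) ends the safety treatment period 30 days after last dose, about when the EOT visit falls. Section 6.4 says the safety analysis covers treatment-emergent events, and section 6.4.1 keeps long-term follow-up events out of the summary tables. Supplement v1.0 tied both the censoring date and the anti-androgen split to the treatment period. On that reading, subjects without fractures means without a fracture on treatment, the windows match and the artefact disappears. The fracture listings are separate outputs and do not define the Kaplan-Meier event.

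This reading is plausible, and it means one cannot claim that the plan expressly counts fractures at any time; the open window is inferred from a missing limit. But no sentence supplies the limit. Version 2.0 rewrote the censoring sentence without adding one and dropped the treatment-period wording from the anti-androgen split. Elsewhere the SAP does write the needed clause: in Appendix 9.1.1, Arm C events after the pooling cut-off are explicitly censored.

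A second reply is that section 6.4.1 intends only treatment-related events to be collected after treatment, so few late fractures would enter. The capture check shows that this does not rescue the rule. It does stand against a different inference: that an analysis to last contact should replace this one. With incomplete collection, that would count unobserved time as fracture-free.

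**Conclusion.** The definition is incomplete in a way that gives a wrong result if programmed literally: curves falling towards zero after EOT, a false median, and a spurious advantage for 12 doses over 6. Under the assumed 1% per month the 12-month share is understated by about 30 percentage points with 6 doses and 5–9 points with 12. The direction and the end at zero follow from the rule once fractures after the last censoring date are counted; the sizes rest on the assumed hazard, survival and stopping.

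A reader might infer more than the documents support. The false contrast lies between A or B and C; A and B have the same planned length and would differ only if early stopping differs. It is not certain that the reported curves will be wrong, because the sponsor may program the on-treatment reading. The immortal-time issue concerns only anti-androgens started after first dose, and its size was not estimated. Safety has no formal tests (section 6.4), and neither co-primary comparison nor its error rate is affected. The point is moderate.

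**What to change.** In Supplemental SAP section 6.5.1:

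- State that an event is a first fracture on or before the EOT visit date (or the fallback date if there is no EOT visit), and that a subject whose first fracture comes later is censored at that date.
- State that the curves have no support beyond EOT in each arm, which is about 5.6 months for 6 completed doses and 11.1 for 12, and that a median not reached is reported as such.
- Add an analysis through follow-up, censoring at the last date fracture status was known, only if fractures were collected completely after treatment in all arms.
- Classify anti-androgen use at first dose, as is already done for bone health agents, or enter use started after first dose as time-varying.

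The cost is a few sentences, one re-derived event flag and date, and a rerun of the overall and subgroup curves. No new data are needed for the on-treatment version.

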6.1.5 Prior and Concomitant Medications

All investigator-reported non-study medications taken before and/or during the study will be coded using the Bayer modified version of World Health Organization Drug Dictionary (WHO-DD) 2005 Q3 and the Anatomical Therapeutic Chemical (ATC) classification system. Coding will include the drug class and generic drug name.

Non-study medications taken before and/or during the study will be categorized as prior medications, concomitant medications, and post treatment medications.

Classifications of prior and concomitant medication as based on [Table 6–1](#).

If a start date is missing, the medication will be assumed to start prior to first dose of study drug. If the end date is unknown and 'ongoing' was not checked in CRF, the medication will be assumed to end at the last visit date, death date or withdrawal from study date, whichever is the latest.

All concomitant medications will be listed, including verbatim descriptions and coded terms, and flags for prior/concomitant/post treatment medications. Prior, concomitant, and post treatment medications will be summarized using frequencies of subjects reporting each drug category and generic drug name. For each subject, multiple records of the same concomitant medication will be counted once within a drug class and generic drug name.

Summaries will also be produced for anti-cancer therapies (systemic therapy, radiotherapy as well as diagnostic and therapeutic procedures). These summaries will be created for ITT population and Week 24 population.

Table 6–1 Medication Classification

	Prior to study drug	Study drug started	Treatment with study drug	Study drug stopped	Follow up	Prior Medication?	Concomitant Medication?	Post-treatment Medication?
C1						Yes	No	No
C2						Yes	Yes	No
C3						No	Yes	Yes
C4						Yes	Yes	Yes
C5						No	No	Yes
C6						No	Yes	No
C7						No	Yes	No
C8						No	Yes	No

C1= medication started before study drug administration and ended on or before study drug administration

C2= medication started before study drug administration and ended during study drug administration
C3= medication started on or after study drug administration and ended after study drug administration
C4= medication started before study drug administration and ended after study drug administration
C5= medication started on or after study drug administration and ended after study drug administration

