C6= medication started on or after study drug administration and ended before or on the same date as end of study drug administration
Note: C7 and C8 are covered under C6.

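### Time to fracture is summarized by anti-androgen, enzalutamide and abiraterone use that is not anchored in time, so the descriptive curves can be distorted in either direction

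*SAP*

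**What the plan says.** Supplemental SAP v2.0, section 6.5.1, fixes the time origin: "Time to fracture is defined as the time (months) from the first dose date to the date of first fracture". On censoring it says "Subjects without fractures are censored at either end of treatment (EOT) visit date", or at the last visit before active follow-up if there was no such visit. Kaplan-Meier quartiles, 80% and 95% confidence intervals and curves are planned.

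The same approach is then applied to subgroups. For bone health agents the grouping is fixed at the start: "Time to fracture will also be summarized for subjects with/without BHA use at baseline". For the three hormonal drug groupings it is "with/without concomitant use of anti-androgen, enzalutamide, and abiraterone by same approach mentioned above", with no time point.

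The only definition of concomitant use is in the main SAP, section 6.1.5, Table 6-1. Two of the classes marked as concomitant cover drugs first taken on treatment:

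- One class is for drugs that outlast radium-223: "C3= medication started on or after study drug administration and ended after study drug administration".
- The other class is for drugs that do not outlast it: "C6= medication started on or after study drug administration and ended before or on the same date as end of study drug administration".

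Supplemental SAP v1.0, now superseded and cited here only for meaning, grouped by "use of concomitant anti-androgen, enzalutamide and abiraterone during the treatment period".

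**The concern.** A Kaplan-Meier curve that starts at first dose needs groups that are known at first dose. Here a subject who begins enzalutamide in month 4 counts as a user from day 1. Two things can go wrong.

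- If a fracture ends radium-223, a subject with an early fracture has no further chance to become a user. Later starters must have been fracture-free until they started, so users look better.
- If a fracture makes it more likely that one of these drugs is started while treatment continues, the subject becomes a user because of the fracture. Users then look worse.

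In addition, nothing stops a fracture that happened before the drug from being counted in the drug's group. This is the document's only summary of time to fracture by these drugs, and the supplement's introduction says its analyses may go into a submission or the study report. Curves shown side by side could suggest protection or harm where there is neither.

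**Working it through.** The documents give no figure for this analysis, so there is nothing to reproduce. The check has two parts.

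**1. Reading the text.** The clock starts at first dose. Concomitant use includes drugs started on or after study drug (Table 6-1, C3 and C6). No landmark, time-dependent or start-before-fracture rule is given. Membership can therefore be decided after time zero and after the event. Table 6-1 words C5 the same as C3 but marks C5 as post-treatment only. The check takes C5 to mean drugs started after study drug ended, which do not make a subject a user.

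**2. Illustration with no true drug effect.** From the SAP: 28-day dosing and a treatment period running to 30 days after the last dose (main SAP, section 6.4.1). The windows are:

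- 6 doses: 5 × 28 + 30 = 170 days, about 5.6 months
- 12 doses: 11 × 28 + 30 = 338 days, about 11.1 months

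Assumed, not from the documents: fracture hazard λ = 0.02 per month, share using at first dose p = 0.15, later start rate σ = 0.04 per month, other discontinuation δ = 0.06 per month. All times are exponential. The table gives the simulated ratio of fractures per person-month, ever-users over never-users.

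| Link between fracture and drug use | 6 doses | 12 doses |
|---|---|---|
| None | 1.00 | about 1.0 |
| Every fracture ends treatment | 0.67 | 0.58 |
| Half of fractures end treatment | 0.83 | 0.77 |
| Fracture triples the start rate | 1.68 | 1.93 |
| Half end treatment, start rate doubles | 0.97 | 0.93 |
| Half end treatment, start rate triples | 1.11 | 1.08 |
| Any of these, grouped by use at first dose | 0.99–1.01 | 0.99–1.01 |

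Repeat simulation runs moved individual entries by up to about 0.02.

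**Share of user fractures that precede the drug, no link.** This has a closed form. Expected fractures per randomized subject in the user group:

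- Users at first dose: p · λ/(λ+δ) · (1 − e^(−(λ+δ)T))
- Later starters, fracture after start: (1−p) · [λ/(λ+δ) · (1 − e^(−(λ+δ)T)) − λ/(λ+δ+σ) · (1 − e^(−(λ+δ+σ)T))]
- Later starters, fracture before start: (1−p) · λ · σ/(σ+δ) · [(1 − e^(−(λ+δ+σ)T))/(λ+δ+σ) − e^(−(σ+δ)T) · (1 − e^(−λT))/λ]

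With the numbers put in:

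- 6 doses: 0.0135 + 0.0074 + 0.0071 = 0.0280; share 0.0071/0.0280 = 25%
- 12 doses: 0.0221 + 0.0208 + 0.0194 = 0.0623; share 0.0194/0.0623 = 31%

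**Different assumptions.** A second set used fracture risk of 5%, 10% or 20% over the period, 10% users at first dose, a further 10% or 30% risk of starting, and no other discontinuation. The ratios were:

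- 0.54 to 0.75 if fracture ends treatment
- 1.52 to 2.07 if it triples the start rate
- 0.97 to 1.02 with no link, with 23% to 36% of user fractures preceding the drug
- 0.97 to 1.03 in every scenario when use was treated as time-dependent

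**The case against.** The strongest reply is that this is a descriptive safety summary. The supplement says time to fracture will be summarized. No hazard ratio or test between users and non-users is planned, and main SAP section 6.4 rules out formal tests for safety endpoints. A reader might infer that the plan formally compares users with non-users; it does not. That limits the consequence but does not repair the grouping: medians, intervals and curves per group are there to be set side by side.

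A reader might also infer that the curves will certainly be biased. The documents do not support that. Nothing shown says that a fracture ends treatment or prompts these drugs. With no such link the ratio is about 1.0, and when the two mechanisms act together they largely offset each other. This objection stands, and the bias is stated here as conditional. What remains even then is that fractures before the drug are counted under the drug.

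Use at any time on treatment is an inference: the current sentence gives no period and does not cite Table 6-1. The inference is reasonable, because that table holds the only definition and v1.0 named the treatment period. Even on the narrowest view the current wording leaves the groups undefined in time.

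Finally, the SAP is not blind to the issue elsewhere. Main SAP section 6.6 has a baseline subgroup for prior abiraterone or enzalutamide on SSE-FS and OS, and section 6.2.1 allows non-study systemic anti-cancer therapy as a time-dependent covariate for SSE-FS, which counts symptomatic pathological fractures. Neither carries over to time to fracture, but both show that the remedy is already in the sponsor's hands.

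**Conclusion.** The point holds as a defect in how the groups are formed. The summary uses information from after time zero and can put fractures in the user group that occurred before the drug. The direction of any distortion is not known. Under the assumed rates, one-sided links give 0.67 and 0.58 or 1.68 and 1.93 (6 and 12 doses) with no true effect, mixed links give 0.93 to 1.11, and no link gives about 1.0. The share of user fractures preceding the drug, 25% to 31% with no link, also rests on those rates.

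Two stronger readings are not supported. The distortion need not be larger in Arm C because treatment is longer: it is in the one-sided scenarios with constant monthly rates, but in one mixed case it is smaller (1.08 against 1.11), and with risks fixed over the whole period the two windows give nearly the same ratios. Nor does the point touch the co-primary SSE-FS results. It is worth correcting because the correction is simple, not because it threatens the trial's main conclusions.

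**What to change.** In Supplemental SAP v2.0, section 6.5.1, define the anti-androgen, enzalutamide and abiraterone groups by use at the first dose (yes/no), as the same sentence already does for bone health agents. With groups fixed at time zero, the illustration gives a null ratio of 0.99 to 1.01 in every scenario.

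Optionally, as a supportive analysis, treat later starts as time-dependent exposure, counted from the drug's start date, with starts after the first fracture ignored. Pool the arms for this, because events are few. With 360 subjects randomized 1:1:1 there are 120 per arm, and 15% of 120 is 18 users at first dose. At the assumed rates their expected fractures are 18 × 0.25 × (1 − e^(−0.08 × 5.6)), about 2 with 6 doses, and 18 × 0.25 × (1 − e^(−0.08 × 11.1)), about 3 with 12. A model by arm would say little.

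The cost is a change of wording and minor programming; the classification in Table 6-1 already relies on medication start dates. The downside is a smaller user group, and the curves by use at first dose will not describe subjects who start one of these drugs later.
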